#### 4.8 Other analyses

For the health economics analyses, EQ-5D-5L index score will be calculated from individual health profiles using UK preference weights. Mean, standard deviation (SD), minimum, median, and maximum scores will be provided for the study population by visit and by randomised treatment. The EQ VAS score (between 0 and 100) will be summarised using mean, SD, minimum, median and maximum scores by visit and by randomised treatment. Patients who are dead at the time of sampling will be assigned a zero index score and a missing VAS response. The numbers and rates of missing data will be reported per measure for each visit.

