
No formal cost-effectiveness analysis is planned, however, if data quality allows, an exploratory estimate of the incremental Quality Adjusted Life Years (QALYs) (at 180 days) and secondary care costs (at 30 days) will be made using the EQ-5D-5L. QALYs will be calculated by estimating a combined survival function and HRQoL function using the EQ-5D. Costs will be estimated by assigning national standard unit costs to inpatient stays (critical care and general ward level), readmissions and additional high costs activities observed in the study. Baseline (pre-admission) HQoL will be estimated using age/sex matched population reference data. In sensitivity analysis, surviving patients or proxies will be asked to provide a retrospective estimate of 1 month pre-admission modified EQ-5D-5L responses.

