## 3 Overall Statistical Principles

The intention-to-treat (ITT) population will include all patients who have been randomised into this trial, and who did not withdraw consent for any of their data to be stored in the trial database. Patients will be analysed in the group to which they were allocated, regardless of the

intervention they actually received. Analyses will be based on the ITT population, unless otherwise specified; in addition, we will explore the influence of adherence on the range of treatment estimates using a suitably specified per-protocol approach (see Section 4.6, analysis (a)).

Safety data will in the first instance be analysed according to treatment received, and will also be summarised descriptively according to an intention to treat approach.

In general terms, categorical data will be presented using counts and percentages, whilst continuous variables will be presented using the mean, median, standard deviation (SD), minimum, maximum, lower and upper quartiles and number of patients with an observation (N). Data will be split by intervention group and time point where applicable.

All applicable statistical tests will be 2-sided and will be performed using a 5% significance level – but all such tests of hypothesis will be informal and interpreted descriptively. 95% (2-sided) confidence intervals (CIs) will be presented.

Where there is missing data for an outcome variable, in the first instance, those records will be removed from any statistical analysis relating to that outcome variable (complete case analysis), unless otherwise specified. In tabulations, numbers of missing observations will be provided, but percentages will not include them.

Distributional assumptions underlying the statistical analyses may be assessed by visual inspection of residual plots. Normality may be examined by normal probability plots. If the distributional assumptions for the parametric approach are not satisfied, further data transformation (to alleviate substantial skewness (i.e. normalizing) or to stabilise the variance), or other suitable methods will be considered. This will be documented in the statistical results report together with the reasoning supporting the action taken, if applicable.

Sites may be categorised into small sites (less than 10 participants recruited) versus big sites (10 or more participants recruited).

All analysis and data manipulation will be carried out using SAS [1] unless otherwise stated.

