Qualitative or health economic analysis will not be covered by this SAP. However, data from the statistics report may be used for health economics analyses.

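### The SAP's zero score for deaths and its complete-case rule together over-represent deaths in the mean EQ-5D index whenever survivor response is incomplete

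*SAP*

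**What the plan says.** SAP 4.8 describes the EQ-5D-5L summaries prepared for the economists, by visit and randomised arm. Its rule for deaths is "Patients who are dead at the time of sampling will be assigned a zero index score and a missing VAS response". It adds that "The numbers and rates of missing data will be reported per measure for each visit". It gives no rule for survivors who do not respond, so the general rule in SAP 3 applies to them: in the first instance "those records will be removed from any statistical analysis relating to that outcome variable (complete case analysis), unless otherwise specified".

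The questionnaire goes to the first 50 patients randomised (SAP 4.6, row 8). Non-response is expected. Protocol 3 plans two mailings and then telephone contact, and Protocol 7.1 says that an unreturned questionnaire is not a deviation. Protocol 7.1 also has vital status checked before a participant is contacted, so deaths should be known more completely than survivors' utility.

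On QALYs, Protocol 10.2 says "QALYs will be calculated by estimating a combined survival function and HRQoL function using the EQ-5D", introduced by "No formal cost-effectiveness analysis is planned, however, if data quality allows, an exploratory estimate". SAP 3 says "Qualitative or health economic analysis will not be covered by this SAP", but also that "data from the statistics report may be used for health economics analyses".

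**The concern.** The two rules treat patients unequally. A death is always scored; a survivor is scored only if a form comes back. The mean index is then neither a mean among survivors nor a mean over all patients randomised. It is a mixture whose weight on death depends on the response rate. Two arms with the same mortality and the same health among survivors would report different means if their response rates differed.

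The missing-data figures are affected too. A death counts as observed for the index and as missing for the VAS, so neither missing rate on its own gives response among survivors. That rate is what a definitive trial would need. Data completeness is a secondary endpoint here, and SAP 4.6(d) intends the missing-data patterns to guide handling in the confirmatory trial.

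**Working it through.** The documents state no EQ-5D figure, so there is nothing to reproduce. The inputs below are assumptions unless a source is named.

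- d, proportion dead at the visit. No 180-day figure is given. Protocol 1.1 cites about 20% during index hospitalisation, and Protocol 10.1 uses 35% and 18% at 30 days. These serve as proxies, with 25% as a middle value.
- r, response among survivors: assumed 50% to 100%.
- u, mean index among survivors: assumed 0.65, with 0.60 and 0.70 as a range.

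**Formulas**, if non-responding survivors resemble responders:

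- Deaths as a share of scored records = d / (d + (1−d)r)
- Mean under the SAP rules = (1−d)r·u / (d + (1−d)r)
- Mean over all randomised = (1−d)u

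**One arm, d = 0.25, r = 0.60, u = 0.65.** Responding survivors are 0.75 × 0.60 = 0.45 of patients, and scored records are 0.25 + 0.45 = 0.70. Deaths are 0.25/0.70 = 36% of scored records instead of 25%. The SAP mean is 0.45 × 0.65/0.70 = 0.418, against 0.75 × 0.65 = 0.488.

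**Equal arms, unequal response (d = 0.25, u = 0.65).** At 70% response: 0.525 × 0.65/0.775 = 0.440. At 50%: 0.375 × 0.65/0.625 = 0.390. The spurious difference is about 0.05.

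**Unequal mortality, 35% v 18%, r = 0.60 in both arms, u = 0.65.** SAP means: 0.39 × 0.65/0.74 = 0.343 and 0.492 × 0.65/0.672 = 0.476. The difference is 0.133, against 0.17 × 0.65 = 0.111, so it is 21% too large.

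**Range over the assumptions:**

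| Dead | Response | Deaths among scored | SAP mean, u = 0.60 | SAP mean, u = 0.70 |
|---|---|---|---|---|
| 20% | 100% | 20.0% | 0.480 | 0.560 |
| 20% | 80% | 23.8% | 0.457 | 0.533 |
| 20% | 60% | 29.4% | 0.424 | 0.494 |
| 20% | 50% | 33.3% | 0.400 | 0.467 |
| 35% | 100% | 35.0% | 0.390 | 0.455 |
| 35% | 80% | 40.2% | 0.359 | 0.418 |
| 35% | 60% | 47.3% | 0.316 | 0.369 |
| 35% | 50% | 51.9% | 0.289 | 0.337 |

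The 100% rows are the correct all-randomised means, because with full response there is no distortion.

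**Non-responders sicker than responders.** Keep d = 0.25, r = 0.60 and responders at 0.65. If non-responding survivors average 0.418, the all-randomised mean is 0.75 × (0.60 × 0.65 + 0.40 × 0.418) = 0.418, and the SAP mean has no bias. If they average 0.30 (assumed), it is 0.75 × (0.39 + 0.12) = 0.383, and the SAP mean of 0.418 is too high.

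**Missing rates, d = 0.25, r = 0.60.** The index is observed in 0.25 + 0.45 = 70% of patients and the VAS in 45%. Survivor response is 60%, which neither figure shows.

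**The case against.** Four points can be made for the plan as written.

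- **A low bias is not certain.** This stands. The direction depends on how ill the non-responding survivors are, as the working shows. It limits what can be said about the mean, but not the over-representation of deaths, which follows from the counts alone. The same caution applies to the remedy: weighting the responders' mean by survival is right only if response is unrelated to health among survivors, or is made so by adjustment.
- **Much can be recovered from the tables.** Missing counts are reported per measure and visit. The index and VAS counts should differ by the number of deaths, apart from partly completed forms, so a careful reader could back out survivor response and survivor means. This stands in part. It is better to report those figures directly, and the complete-case rule is in any case described only as a first step.
- **Zero for the dead is an accepted convention.** This stands. Zero is not an error when survival enters once, and a survivor-only VAS needs only a label. The difficulty is the zero rule combined with dropped survivors.
- **The effect is small against the noise.** This stands. Take 25 patients per arm, 70% scored (17.5) and an assumed survivor SD of 0.25. The variance of the scored index is 0.643 × (0.65² + 0.25²) − 0.418² = 0.137, so its SD is 0.370. The standard error of an arm difference is 0.370 × √(2/17.5), about 0.12. The spurious 0.05 is about 0.4 of that, and 0.133 v 0.111 about 0.2.

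A reader might also infer that the QALY method counts every death twice, by applying a survival function to means that already contain zeros. The documents do not say this. A combined function can be survival times survivors' utility, or individual profiles with zero after death, and each counts death once. Health economics lies outside the SAP, and SAP 6 provides an analysis data set, so the economist need not work from the reported means. Double counting is only a risk if those means are multiplied by survival again.

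**Conclusion.** The point holds for the reported mean index. Under the stated rules, deaths are over-represented in each arm's mean whenever a survivor does not respond, and the protocol expects some not to. If non-responders resemble responders, the mean is too low: by 0.023 to 0.037 at 80% response and 0.080 to 0.118 at 50%, over the mortality and utility values in the table. Arm differences also move with response and mortality. These sizes rest on assumed utility, response and 180-day mortality, and on non-response being unrelated to health among survivors. If non-responders are sicker, the bias shrinks, vanishes or reverses.

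It would go too far to say that the index is necessarily biased low, or that the QALY estimate is planned with death counted twice; the documents support neither. The consequence is limited to descriptive and exploratory results in the first 50 patients. The primary outcomes are unaffected. It is still worth correcting, because these summaries and completeness figures are meant to inform a larger trial.

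**What to change.** Amend SAP 4.8 as follows.

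1. Report the index and the VAS among survivors at each visit and by arm. Give response as a proportion of survivors, with deaths shown separately.
2. If an all-randomised mean index is wanted, form it as the proportion alive, from the vital status of all 50 patients, times the mean index of responding survivors. Alternatively, impute surviving non-responders before adding zeros for the dead. State that both options assume data missing at random among survivors.
3. As a safeguard at the hand-over to the economists, state that death enters the QALY calculation only once.

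The cost is a few sentences of SAP text and a few lines of code. No new assessment is needed. The schedule in Protocol 7.1 marks mortality only to Day 90, so the 180-day proportion alive would come from the vital-status check already planned before contact, and its result should be recorded for all 50.

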#### 4.9 Data listings

The following data listings will be provided, ordered by randomised treatment group, participant number and date:

1. Protocol violations
2. Protocol deviations
3. Adverse events
4. Suspected unexpected serious adverse reactions (SUSARs)

### 5 Validation and QC

Data collection and quality checks will be carried in accordance to SOP ECTU\_DM\_01. The report will be read and sense checked by a second statistician, who will also reproduce independently the primary outcome analysis (Section 4.4 only).

### 6 Data sharing

A file, or set of files, containing the final analysis data set will be prepared, along with a data dictionary. These will be made available to the Chief Investigator at the end of the analysis phase.

### 7 List of Abbreviations

A	B
Abbreviation	Full name
AE	Adverse Event
ALT	Alanine aminotransferase
AR	Adverse Reaction
bpm	Beats per minute
°C	Degrees centigrade
CHD	Coronary heart disease
CI	Confidence interval

A	B
CRP	C reactive protein
CNS	Central nervous system
CVD	Cardiovascular disease
ECTU	Edinburgh Clinical Trials Unit
ED	Emergency department
eGFR	Estimated glomerular filtration rate
GCS	Glasgow coma scale
HAS	5% Human Albumin Solution
HDU	High dependency unit
HRQol	Health Related Quality of Life
ICU	Intensive care unit
IMP	Investigational medicinal product
IQR	Interquartile range
ITT	Intention to treat
KG	Kilogram
L	Litre
N	Number
MI	Myocardial infarction
mL	Millilitre
mmHg	Millimetres of mercury
qSOFA	Quick sepsis-related organ failure assessment
NEWS/NEWS2	National early warning score
SAE	Serious Adverse Event
SAP	Statistical analysis plan
SAR	Serious Adverse Reaction

A	B
SAS	Statistical Analysis Software (a proprietary analysis package) [1]
SD	Standard deviation
SOP	Standard Operating Procedure
SUSAR	Suspected Unexpected Serious Adverse Reaction
WCC	White cell count
Y/N	Yes/No

